A Randomized Trial of Transcutaneous Nerve Stimulation for Overactive Bladder Patients

[name]

Assistant Professor, Western University

NCT 02511717

March 1 2016

Statement of Objective

To determine the efficacy of transcutaneous tibial nerve stimulation (using skin patch electrodes) for the treatment of women with clinical symptoms of overactive bladder.

Background

Overactive bladder is a clinical diagnosis characterized by “urinary urgency, often with frequency and nocturia, with or without urgency urinary incontinence”². Approximately 16% of adult women meet the clinical definition for overactive bladder, and approximately 1/3 of them will have urgency incontinence^{3,4}. While a small proportion of patients do see their symptoms resolve after a year, for the vast majority this is a chronic condition^{4,5}. Although it is not inherently dangerous, overactive bladder is an important condition given its wide-ranging impact on overall quality of life and mental health³. The magnitude of impact across different domains of quality of life is similar to chronic diseases such as diabetes⁶. In addition, the financial impact is substantial; in the United States this has been estimated at \$12 billion annually⁷.

Hypothesis

I hypothesize that the study protocol of transcutaneous tibial nerve stimulation performed at home during 30 minute sessions, 3x/week, for 12 weeks will be associated with a statistically significant improvement in overall bladder symptoms.

Design and methodology

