Study design: This is a randomized, double blind, sham controlled clinical trial. The primary intervention is 30 minute sessions, 3x/week, for 12 weeks of transcutaneous tibial nerve stimulation sessions carried out at home. The sham intervention will consist of the same treatment schedule, except with the application of transcutaneous nerve stimulation to the lateral aspect of the lower leg, away from the tibial nerve. Patients will undergo a 12 week treatment course. The patient and the treating physician will be blinded to the group assignment of the patient. Randomization will be done using a random number generator, and study assignment will only be released at the end of the study. Only the study nurse instructing the patient on placement of the study electrodes will know the patient assignment. The effectiveness of our sham protocol will be evaluated with a question during week 2-3 asking if they think they are in the active or sham group. The study visit schedule is outlined in more detail in Appendix 2.

Inclusion criteria

1. Female, >18 years of age, with the clinical diagnosis of overactive bladder (based on the current ICS definition²).
2. Failure of behavioral measures and pharmacologic therapy to adequately control overactive bladder symptoms.
3. Baseline patient perception of bladder condition score of 2 or higher.

Exclusion criteria

1. Current or previous percutaneous or sacral neuromodulation therapy
2. Stress predominant urinary incontinence

3. Newly added bladder medication or dose change with the last 2 months (Tamsulosin, Silodosin, Alfuzosin, Terazosin, Baclofen, Diazepam, amitriptyline, imipramine, DDAVP, tolterodine, oxybutynin, fesoterodine, darifenacin, solifenacin, trospium, mirabegron)
4. Intravesical botulinum toxin use within the last 1 year
5. Implanted pacemaker or defibrillator
6. History of epilepsy
7. Unable or unwilling to commit to study treatment schedule
8. Pregnant, or possible pregnancy planned for the duration of the study period
9. Active skin disease of the lower legs (dermatitis, cellulitis, eczema, trauma)
10. Documented allergy to patch electrodes or their adhesive
11. Abnormal sensory function of the lower limb
12. Metallic implant within the lower limb

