2. 3-day voiding diary parameters (daily voiding frequency, functional bladder capacity, mean voided volume, longest time between voids, nocturia, number of urgency incontinence episodes). This is a valid and reliable measure of urinary symptoms³².
3. Quantification of urinary incontinence with 24hr pad weights. This is stable, reliable and responsive measure of the degree of urinary incontinence^{33,34}.
4. Physician assessment of benefit will be completed based on a standard clinical history at study visit 3 (end of study), and graded on a 7 point global response assessment.

Data Analysis and Sample Size

Analysis of our primary outcome will be an intention to treat analysis (using the chi squared test) based on the proportion of patients classified as a responder using the change in the patient perception of bladder condition. A secondary analysis, based on a per protocol analysis (for efficacy) will be performed for patients who completed at least 80% of the treatment sessions for at least 20 min each (determined from patient completed treatment diary, and electronic usage log in the TENS device). Secondary endpoints will be analyzed as appropriate using the students t-test or chi squared test. All data analysis will be carried out using SAS 9.2.

Using previous percutaneous tibial nerve stimulation studies as a guide²³, we estimate 20% of sham patients and 60% of actively treated patients will be responders. Using the Chi-square test, a two-sided alpha of 0.05, and 80% power, 27 patients per group will be required. Our final sample size, adjusting for a 10% dropout rate, is 60 (30 per group). Our sample size calculation is based on our intention to treat analysis.

References

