Appendix 2. Study schedule.

STUDY SCHEDULE	Visit 1 Screening	Visit 2 Randomization	Telephone Followup	Visit 3 End of study
Visit Windows	1- 4 weeks prior to Randomization	Week 0	Every 2-3 Weeks	12-13 Weeks
Documentation of Consent	X			
Medical History and Physical Exam	X			
Inclusion/ Exclusion Criteria Review	X			
Medication and Health Review	X			X
Urine Pregnancy Test	X			
PPBC Questionnaire	X		X (week 6-7 only)	X
OAB-q SF Questionnaire	X			X
3 day Voiding diary	Diary Provided	Completed diary returned & new one provided for Visit 3		Completed diary returned
24hr Urinary Pad test	Supplies Provided with instruction	Pads Returned & new ones provided for Visit 3	Pad test done 1-7 days prior to visit 3	Pads Returned
Randomization		X		
Initial 30 minute treatment session in clinic with nurse supervision		X		
Assessment of treatment masking			X (week 2-3 only)	
Assessment of compliance, review instructions, address any adverse events or questions			X	
Physician assessment of benefit				X

Appendix 3. Patient perception of bladder condition. Scored 0 (no problems) to 5 (severe problems).

(PPBC)

Which of the following statements describes your bladder condition best at the moment? Please mark “X” in one box only.

My bladder condition does not cause me any problems at all.

My bladder condition causes me some very minor problems.

My bladder condition causes me some minor problems.

My bladder condition causes me (some) moderate problems.

My bladder condition causes me severe problems.

My bladder condition causes me many severe problems.

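### The 24-hour pad weight would be compared by a t-test on raw grams; a baseline-adjusted log-scale analysis should be pre-specified instead (minor)

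*Combined protocol and SAP*

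**What the plan says.** Item 3 of the secondary outcome measures is "Quantification of urinary incontinence with 24hr pad weights". The only analysis rule for it is in Data Analysis and Sample Size: "Secondary endpoints will be analyzed as appropriate using the students t-test or chi squared test". The words on appropriateness choose between the two named tests. No rank test, transformation, baseline adjustment or distribution check is mentioned, and the plan does not say whether the Visit 3 weight or the change is the outcome.

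Leakage is not needed for entry. Inclusion criterion 1 asks for a woman "with the clinical diagnosis of overactive bladder (based on the current ICS definition", and the Background section says of women with overactive bladder that "approximately 1/3 of them will have urgency incontinence".

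A pre-treatment weight is available. Supplies are given at Visit 1, and the Visit 2 entry in Appendix 2 reads "Pads Returned & new ones provided for Visit 3".

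The sample size is set on the primary outcome alone: "Using the Chi-square test, a two-sided alpha of 0.05, and 80% power, 27 patients per group will be required".

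**The concern.** A t-test on grams compares means. When many patients sit at or near zero and a few leak heavily, the heavy leakers dominate both the mean and its standard error. At about 27 to 30 per arm the test then tends to be conservative and weak. Two obvious remedies do not fully solve this. Restricting to wet patients leaves the skew, and ANCOVA on raw grams recovers only part of the loss.

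Pad weight is the one listed outcome that measures leakage by weight rather than by patient report or physician grading. At stake is a real reduction reported as no difference, or a choice of method made after the data have been seen.

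**Working it through.** **The plan's own figure.** The response rates are given as "we estimate 20% of sham patients and 60% of actively treated patients will be responders". Without continuity correction, n = [1.96·√(2·0.4·0.6) + 0.842·√(0.2·0.8 + 0.6·0.4)]² / 0.4² = 22.3 per group. With it, n = (22.33/4)·[1 + √(1 + 4/(22.33·0.4))]² = 27.1, which matches the stated 27. Then 27/0.9 = 30 per group, 60 in total. This concerns the primary outcome only. The documents state no power for pad weight.

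**Inputs taken from the documents.** 27 per arm; two-sided 5%; t-test; wet share of one third as one scenario.

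**Assumptions, because the documents give no figure.** Wet weights are log-normal with log SD 0.8 to 1.5, or exponential. For the log-normal, SD/mean = √(exp(s²) − 1), which is 0.95, 1.8 and 2.9 at s = 0.8, 1.2 and 1.5. Within-patient log SD is 0.4 or 0.7. Dry patients weigh 0-2 g, or exactly 0. Final weight is 40% of baseline on active and 90% on sham.

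**Base case** (simulated power; log SD 1.2, within-patient log SD 0.4 at both visits, dry 0-2 g):

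| Analysis | 1/3 wet | 2/3 wet | all wet |
|---|---|---|---|
| t-test, change | 17% | 35% | 49% |
| Wilcoxon, change | 27% | 69% | 88% |
| t-test, final weight | 8% | 22% | 39% |
| Wilcoxon, final weight | 6% | 17% | 60% |
| ANCOVA, log(grams + 1) | 46% | 94% | 100% |

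On change, the t-test keeps 17/27 = 63%, 35/69 = 51% and 49/88 = 56% of the rank test's power.

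**Varying the assumptions (change from baseline, t-test against Wilcoxon; three figures are 1/3, 2/3 and all wet).**
- Within-patient log SD 0.7: 9/17/23% against 17/39/52%. The t-test keeps 53%, 44% and 44%.
- Exponential wet weights: 24/47/66% against 25/66/88%. It keeps 96%, 71% and 75%.
- Log SD 0.8, one third wet: 27% against 27%, so no loss.
- Log SD 1.5, all wet, in a variant with the active median at 0.35 of sham: 14.7% against 40.9%. It keeps 36%.
- Dry patients at exactly 0 g, log SD 1.2: 17/36/50% against 38/72/87%. ANCOVA on raw grams gives 39/70/85%, and ANCOVA on log(grams + 1) gives 79/99/100%.

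**No treatment effect.** Rejection rates are about 2-4% for the t-test on change, 4-5% for Wilcoxon and 4-6% for ANCOVA on log(grams + 1).

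**Final weight behaves differently.** With all patients wet and the active median half of sham, t-test against Wilcoxon is 77 v 86%, 52 v 68%, 30 v 49% and 18 v 37% at log SD 0.8, 1.0, 1.25 and 1.5. With two thirds at zero in both arms it is 14.5 v 6.6%, 10.4 v 6.0%, 6.6 v 5.7% and 4.5 v 5.3%, so the t-test leads in three of four.

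**The Hodges-Lehmann difference over all patients.** It is the median of all between-arm pairs. At one third wet, (2/3)² = 4/9, or 44%, of pairs are dry against dry. In simulation the estimate was about −0.7 g whether the true mean difference was −7.5 g or −18 g, and exactly 0 when dry patients were at exactly 0 g.

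**The case against.** The strongest objection is that no size for this loss can be derived from the documents. That stands. A reader might infer that the t-test costs half the power. That figure needs assumed skew and wet shares. It is not a ceiling, and under mild skew the loss disappears. In one variant, with log SD 0.8, one third wet and measurement noise at the final visit only, the t-test on change led by 48% to 35%. The one-third figure itself describes women with overactive bladder in general, not this treatment-refractory sample.

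A reader might also infer that any rank test is better. On final weight with many dry patients it is not, because ties at zero weaken it. The gain is for ranks on change. Even there, at one third wet the base-case rank test has only 27% power, so switching to Wilcoxon alone would still miss a real effect about three times in four. An all-patient Hodges-Lehmann estimate could also sit near 0 g beside a significant p-value.

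Finally, nothing suggests excess false positives, and no secondary endpoint is powered. Both are true, and they hold the severity down. They do not remove the gap: for a continuous weight the plan permits only the t-test and leaves the outcome undefined.

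**Conclusion.** The point holds as a minor one. As written, pad weight would be compared by a t-test on raw grams. Under log-normal or exponential wet weights, 27 per arm and a 40% v 90% effect, the t-test on change gives up from almost nothing (mild skew, one third wet) to more than half (strong skew, or noisier measurement) of the power of a rank test on change. It is slightly conservative under no effect. ANCOVA on log(grams + 1) did better than either in the settings run, with type I error near nominal. Its figures also depend on the assumed typical wet weight in grams, which the documents do not give.

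The documents do not support a fixed figure such as half the power, a general preference for ranks, or any doubt about the primary result. The responder analysis and the 60-patient sample size are unaffected.

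**What to change.** In Data Analysis and Sample Size, before assignments are released, add that 24-hour pad weight is analysed by ANCOVA of log(grams + 1) at Visit 3 on treatment and baseline log(grams + 1), with the baseline from the pads returned at Visit 2. Report the effect as a ratio on the (grams + 1) scale with a 95% CI. Name a Wilcoxon rank-sum test on change from baseline, not on final weight, as the supporting analysis. Give medians and any Hodges-Lehmann difference only for patients wet at baseline, and fix the definition of wet in advance.

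Limit the change to pad weight. A check on simulated 3-day urgency incontinence counts found no gain from ranks (t-test v rank test 27 v 27%, 65 v 61%, 86 v 84%).

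The cost is a sentence or two and no new data. The effect becomes a ratio rather than a mean difference in grams, and the added 1 g is a convention. Mean grams by arm can still be shown descriptively.

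### Does leaving the version of the chi-squared test unstated undermine the primary analysis or the 27 per group?

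*Combined protocol and SAP*

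**What the plan says.** The section Data Analysis and Sample Size fixes the primary analysis in one sentence: "Analysis of our primary outcome will be an intention to treat analysis (using the chi squared test"), applied to the proportion of responders. The planning rates are stated next: "we estimate 20% of sham patients and 60% of actively treated patients will be responders". The sizing sentence reads "Using the Chi-square test, a two-sided alpha of 0.05, and 80% power, 27 patients per group will be required", and the enrolment target follows: "Our final sample size, adjusting for a 10% dropout rate, is 60 (30 per group"). The section adds that the sizing rests on the intention-to-treat analysis, and it names SAS 9.2 as the software. For the remaining outcomes it says "Secondary endpoints will be analyzed as appropriate using the students t-test or chi squared test".

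The chi-squared test is thus named for both sizing and analysis, without a qualifier in either place. Nothing elsewhere in the document says which version is meant.

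**The concern.** For a two-by-two table of this size, three tests are in common use: the uncorrected (Pearson) chi-squared test, the same test with a continuity correction, and Fisher's exact test. They do not need the same number of patients and do not always reach the same conclusion.

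Two things look wrong. First, the usual uncorrected formula does not give 27 at the stated rates, alpha and power; it gives 23. The figure of 27 fits the corrected or exact test, so the sizing seems to rest on one version while the analysis sentence commits to none. Second, some results are significant with one version and not with another. If the choice were made after the data were seen, the threshold for declaring success would not be fixed in advance.

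**Working it through.** **Inputs**, all from Data Analysis and Sample Size: responder rates 0.60 and 0.20, two-sided alpha 0.05 (z = 1.960), power 80% (z = 0.8416), equal groups, 10% dropout. The mean rate is 0.40 and the difference 0.40.

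**Reproducing 27.**

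- Uncorrected formula: n = [1.960 × √(2 × 0.4 × 0.6) + 0.8416 × √(0.6 × 0.4 + 0.2 × 0.8)]² / 0.40² = (1.3579 + 0.5323)² / 0.16 = 22.33, so 23 per group.
- Continuity-corrected formula: n = (22.33 / 4) × [1 + √(1 + 4 / (22.33 × 0.40))]² = 5.583 × 2.2033² = 27.10. This is 27 to the nearest whole number and 28 if always rounded up.
- Dropout: 27 / (1 − 0.10) = 30 per group, 60 in total, as stated.

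**Exact power** at 60% and 20%, found by summing the two binomial distributions over every table significant at 0.05:

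| n per group | Uncorrected | Corrected | Fisher |
|---|---|---|---|
| 22 | 79.1% | 69.1% | 69.1% |
| 23 | 81.9% | 72.7% | 72.7% |
| 26 | 86.7% | 79.9% | 79.9% |
| 27 | 86.8% | 80.2% | 80.2% |
| 30 | 90.5% | 85.1% | 85.1% |

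The first size at or above 80% is 23 for the uncorrected test and 27 for the other two. That 27 came from a corrected or exact method is an inference from this arithmetic; the document does not say so.

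**Can the versions disagree?** Take 14/30 active and 6/30 sham, with sham at its planned 20%. The cross-product difference is 14 × 24 − 16 × 6 = 240, and the product of the margins is 30 × 30 × 20 × 40 = 720,000.

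- Uncorrected: 60 × 240² / 720,000 = 4.80, p = 0.028.
- Corrected: 60 × (240 − 30)² / 720,000 = 3.675, p = 0.055.
- Fisher: p = 0.054.

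At 15/30 against 6/30 all three are significant (0.015, 0.030, 0.029). At 13/30 against 6/30 none is (0.052, 0.096, 0.095). At that sham count the choice moves the threshold by one active responder.

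**How often?** With 30 per arm, 54 of the 31 × 31 = 961 possible tables split the uncorrected and corrected tests, always with the uncorrected one significant. Corrected and Fisher agree in every table at this size. The probability of a split is 5.4% at 60% and 20%, which equals the power difference (90.46% − 85.08% = 5.38%). At 55% and 21%, the Appendix 1 rates for the sham-controlled trial cited as the planning guide, it is 8.4%.

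**Does either version mislead?** Exact type I error with 20% responding in both arms:

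| n per group | Uncorrected | Corrected or Fisher |
|---|---|---|
| 27 | 5.7% | 1.9% |
| 30 | 4.9% | 2.2% |

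Over all common response rates at 30 per arm, the maximum is about 5.5% uncorrected and 2.7% corrected.

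**The case for a change.** The strongest case for a change is that it would be cheap. One phrase would settle the version, no patients or visits would be added, and the success threshold would be fixed beyond dispute. The split is also more likely when the effect is smaller than planned (8.4% against 5.4%), which is where the conclusion is most open to challenge. And on the plain reading, in which an unqualified chi-squared test is the uncorrected one, pairing 27 with 80% understates the power.

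The arithmetic behind all of this stands. What does not stand is that the plan yields a wrong or unsafe result as written. On the plain reading the test is settled, and 27 exceeds the required 23 by four per group, an error in the safe direction. On the other reading 27 is right. The 5.7% type I error applies at 27 per arm, whereas the primary analysis is by intention to treat with 30 per arm, where the figure is 4.9%. Nor is the corrected test clearly better: it guards against an excess that is at most about half a percentage point at 30 per arm, and it costs 5.4 points of power at the planning rates.

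The point also reaches little beyond the primary outcome. The listed secondary outcomes are a questionnaire, diary measures, pad weights and a seven-point physician rating, and none is defined as a responder proportion. Only the per-protocol repeat of the responder comparison clearly shares the open choice.

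**Conclusion.** No change to the plan is needed. The version of the test is a detail left unwritten, of the kind a trial statistician settles before unblinding and reports with the result. Either choice gives a sound analysis: at 30 per arm, power at the planning rates is 90.5% or 85.1%, and type I error with 20% in both arms is 4.9% or 2.2%. No stated figure is missed, because 27 per group is exact for the corrected or Fisher test and conservative for the uncorrected one.

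What remains is a narrow band of results, about 5.4% of trials at 60% and 20% and 8.4% at 55% and 21%, in which the versions fall on opposite sides of 0.05. Choosing between them trades power against a stricter error rate; it does not correct a mistake. These figures assume that all 30 per arm are analysed and that the planning rates, which are not questioned here, are taken as given. A reader who meets a p-value just below 0.05 in the results should check which version was used.

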Intervention: Transcutaneous electrical nerve stimulation is a safe and effective therapy that has been used by physicians and other health professionals for a variety of conditions such as pain and muscle rehabilitation^{26,27}. We will use the EV-906 Digital TENS machine (from Everyway Medical Instruments Co Ltd, Health Canada License #73631). Two adhesive patch electrodes will be applied to one of the patient's lower limb, and the location used will be based on their treatment assignment (active treatment versus sham). The initial treatment will be carried out in the clinic under the supervision of the investigating physician, with training provided for the patient on proper use of the device by the study nurse. The remaining treatments will be detailed on a calendar for the patient, with telephone contact every 2-3 weeks with research staff to assess compliance. When undergoing active treatment, patients will have the electrodes applied posterior to the medial malleolus, and 5-10 cm above the medial malleolus of the same leg, just behind the medial tibial edge. As per previous studies involving transcutaneous posterior tibial nerve stimulation^{25,28,29} and similar to percutaneous tibial nerve stimulation²³, we will use the bipolar stimulation setting, with a frequency of 10 Hz, 200ms pulse, and the amplitude will be titrated up to patient's maximum nonpainful tolerance (between 0.5-10mA). For patients undergoing sham treatment, they will have the patch electrodes placed on the lateral side of the lower limb, and told to keep the current setting stable at 1mA. This will prevent any meaningful stimulation of the tibial nerve, while still delivering a slight tingling sensation to simulate active treatment.

Primary outcome measure: The patient perception of bladder condition (PPBC) is a commonly used measure for global response in overactive bladder studies. It is an ordinal scale from 0-5 (Appendix 3). It is a valid, reliable and responsive single question asking the patient to select the degree of problems associated with their bladder condition³⁰. Patients will be categorized as responders (score improvement by 2 points between screening visit 1 and end of study visit 3) or nonresponders.

Secondary outcome measures:

1. OAB related quality of life (OAB-q SF) Valid, reliable, and responsive tool for assessing symptom bother and OAB related quality of life³¹.

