Appendix 1. Randomized controlled trials evaluating percutaneous tibial nerve stimulation.

Study	Sample	Design	Intervention/Control	Outcome
OrBIT¹	100 adults with urinary frequency >8/day and OAB	Randomized controlled trial. Intention to treat.	PTNS (Urgent PC): 0.5-0mA, 20Hz, unilateral needle electrode, weekly 30 minute sessions x 12 weeks. Control: Tolterodine 4mg OD x 90 days	Intervention: 80% global response assessment moderate or markedly improved Sham: 55% global response assessment moderate or markedly improved. P<0.01
SUmIT²	220 adults with OAB	Randomized controlled clinical trial. Intention to treat.	PTNS (Urgent PC): 0.5-10mA, 20Hz, unilateral needle electrode, weekly 30 minute sessions x 12 weeks. Control: Sham group with identical setup but no active electricity.	Intervention: 55% global response assessment moderate or markedly improved Sham: 21% global response assessment moderate or markedly improved. P<0.001
PTNS versus placebo³	35 women with urodynamic DO and wet OAB	Randomized controlled trial. Intention to treat.	PTNS (Urgent PC): 0.5-10mA, 20Hz, unilateral needle electrode, 30 minute sessions 3x/week x 12 weeks. Control: Sham group with identical setup but no active electricity.	Intervention: 71% global response assessment moderate or markedly improved Sham: 0% global response assessment moderate or markedly improved. P<0.001
PTNS vs Oxybutynin vs Combination for OAB⁴	70 women with OAB	Randomized controlled trial.	PTNS (Urgent PC): 0.5-0mA, 10Hz, unilateral needle electrode, weekly 30 minute sessions x 12 weeks. Comparator 1: Oxybutynin SR 10mg PO OD x 12 weeks Comparator 2: Both PTNS and Oxybutynin x 12 weeks	Significant reduction among all groups, and no difference between groups based on ICIQ-SF score.

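### Does raising 27 to 30 per group for dropout leave the intention-to-treat primary analysis short of its stated 80% power?

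*Combined protocol and SAP*

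**What the plan says.** All the relevant text is in the combined protocol and SAP. Under Data Analysis and Sample Size:

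- Primary analysis: "Analysis of our primary outcome will be an intention to treat analysis (using the chi squared test", applied to the proportion of responders.
- Planning rates: "we estimate 20% of sham patients and 60% of actively treated patients will be responders".
- Size before dropout: "Using the Chi-square test, a two-sided alpha of 0.05, and 80% power, 27 patients per group will be required".
- Size after dropout: "Our final sample size, adjusting for a 10% dropout rate, is 60 (30 per group".
- Basis: "Our sample size calculation is based on our intention to treat analysis".

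Under Primary outcome measure: "Patients will be categorized as responders (score improvement by 2 points between screening visit 1 and end of study visit 3) or nonresponders".

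Appendix 1 lists the sham-controlled study cited for the planning rates as an intention-to-treat trial, with "Intervention: 55% global response assessment moderate or markedly improved Sham: 21% global response assessment moderate or markedly improved". Appendix 2 schedules the Patient Perception of Bladder Condition (PPBC) at screening, once by telephone at week 6-7, and at visit 3.

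The plan does not say how a patient with no visit 3 PPBC is classified, whether 60% and 20% refer to completers or to everyone randomised, or whether the chi-square test carries a continuity correction.

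**The concern.** The paragraph seems to treat the same dropouts in two ways. Dividing 27 by 0.9 is the usual step when 10% of patients will be missing from the test and 27 per group must remain. An intention-to-treat analysis does not lose them: all 60 stay in the denominators. If those without a visit 3 score count as non-responders, both response rates shrink and so does the difference between them, and dividing by 0.9 does not fully make up for that.

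Two things would be at stake. Power for the primary analysis could be below the stated 80%. And with about six dropouts expected (10% of 60) and no written rule, the choice between omitting them and counting them as failures could decide a borderline result.

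**Working it through.** **Inputs.** From Data Analysis and Sample Size: two-sided alpha 0.05, power 80%, rates 60% and 20%, 10% dropout, 30 per group.

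**1. Reproduce 27.** Uncorrected chi-square formula, d = 0.40, mean rate 0.40:

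n = [1.960·√(2·0.40·0.60) + 0.842·√(0.60·0.40 + 0.20·0.80)]² / 0.40² = 22.33, so 23 per group.

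Continuity-corrected formula:

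n′ = (22.33/4)·[1 + √(1 + 4/(22.33·0.40))]² = 27.10, which rounds up to 28.

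Summing binomial probabilities over all possible tables, the corrected test (and likewise Fisher's exact test) has 79.9% power at 26 per group and 80.2% at 27. So 27 is the smallest size reaching 80% with a corrected or exact test. The plain test has 86.8% at 27.

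The plan does not state its route. The uncorrected formula at 54% vs 18% gives 26.70, which also rounds to 27.

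**2. Dropout step.** 27/0.9 = 30.0, as stated.

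**3. Dropouts kept as non-responders.** Assume 60% and 20% are completer rates. Then 0.9 × 60% = 54% and 0.9 × 20% = 18%.

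Uncorrected formula at n = 30, d = 0.36, mean rate 0.36:

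power = Φ{[0.36·√30 − 1.960·√(2·0.36·0.64)] / √(0.54·0.46 + 0.18·0.82)} = Φ(1.02) = 84.6%.

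For the corrected version, replace 0.36 by 0.36 − 1/30: Φ(0.73) = 76.7%. Enumeration is the better figure.

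**4. Enumerated power at 30 per group under each reading.**

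| Reading of 60% and 20% | Rates analysed | Chi-square as named | Continuity-corrected |
|---|---|---|---|
| Completer rates, all dropouts non-responders | 54% vs 18% | 84.6% | 77.5% |
| Completer rates, dropouts respond at half those rates (assumption) | 57% vs 19% | 87.7% | 81.4% |
| Rates for all randomised | 60% vs 20% | 90.5% | 85.1% |

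Only one of the six cells is below 80%. To reach 80% there, the corrected test needs 32 per group (78.6% at 31, 80.8% at 32), or 64 patients.

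**5. How often the handling matters.** Take exactly six dropouts, split between arms by chance, with 60% vs 20% among completers:

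| Test | Dropouts omitted | Dropouts as non-responders | Verdicts differ |
|---|---|---|---|
| Chi-square as named | 86.9% | 84.6% | 4.9% |
| Continuity-corrected | 80.1% | 77.6% | 5.9% |

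Imbalance acts in both directions. For the named test with dropouts as non-responders, power is 90.0% with 2 active and 4 sham dropouts, 85.5% with 3 and 3, and 79.7% with 4 and 2.

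**The case for a change.** The strongest case for a change has two parts.

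First, 27 matches a corrected or exact calculation and not the plain formula at 60% vs 20%. Judged by the method that most directly gives its own figure, the plan has 77.5% for an intention-to-treat analysis with dropouts as failures. Reading 60% and 20% as all-randomised rates does not tidy the paragraph either, because no dropout allowance would then be due. The arithmetic here is right, and the wording of the paragraph remains awkward. But how 27 was obtained does not settle how the data will be tested. The plan names the chi-square test for both sizing and analysis and mentions no correction. A dropout allowance added to all-randomised rates would be a margin of safety, not a loss of power. The 55% vs 21% in Appendix 1 does not show that 60% and 20% are completer rates: the plan says it used earlier studies, in the plural, as a guide, and Appendix 1 also lists a sham-controlled trial with 71% vs 0%.

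Second, the absence of a rule for a missing visit 3 score does not depend on the correction, and it can turn a borderline verdict. That stands as a description. The week 6-7 PPBC also offers an alternative that the plan neither adopts nor excludes. However, the outcome has two classes and response requires a demonstrated improvement at visit 3. A randomised patient with no such score has not met the definition, and intention to treat keeps her in her group. Counting her as a non-responder is the ordinary reading.

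**Conclusion.** No change follows. The claim that the primary analysis misses 80% power is not established, because it needs three conditions together: a continuity-corrected or exact test, 60% and 20% as completer rates, and every dropout a non-responder. The plan states none of them. Even then the gap is 2.5 points (77.5% against 80%). Without the correction, power is 84.6%. With all-randomised rates it is 85.1% even with the correction. These figures assume equal dropout in the two arms and take the planning rates as given. At the 55% vs 21% of Appendix 1, on a different outcome measure, power at 30 per group would be 78.9% with the named test, but that is a question about the assumed effect, not about dropout.

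What remains is missing detail. Writing the rule down would record what the intention-to-treat principle and the responder definition already imply. It would keep the named test and the 60 patients, with power of about 85%. The sentence on the basis of the sample size can fairly be read as saying that the trial was sized for the primary analysis and not for the per-protocol set of patients who completed at least 80% of sessions.
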